5.6.2 Adverse Events

The AE verbatim descriptions (investigator terms from the CRF) will be classified into standardized medical terminology using the Medical Dictionary for Regulatory Activities (MedDRA). Adverse events will be coded to the MedDRA (Version 19.1 or higher) lower level term (LLT) closest to the verbatim term. The linked MedDRA preferred term (PT) and primary system organ class (SOC) are also captured in the database. A treatment-emergent adverse event (TEAE) is defined as an AE that emerges during treatment, having been absent at pretreatment (Baseline) or

- Reemerges during treatment, having been present at pretreatment (Baseline) but stopped before treatment, or
- Worsens in severity during treatment relative to the pretreatment state, when the AE is continuous.

Only those AEs that are treatment-emergent will be included in summary tables.

A subject will be counted only once within an SOC and PT, even if the subject experienced more than 1 TEAE within a specific SOC and PT.

The TEAEs will be summarized by treatment group and E6011 overall. The incidence of follow TEAEs will be reported as the number (percentage) of subjects with TEAEs by SOC and PT:

- TEAEs
- TEAEs by maximum intensity
- Serious TEAEs
- TEAEs leading to study drug withdrawn
- TEAEs leading to interruption of study drug
- TEAEs leading to reduction from study drug
- Treatment Related, TEAEs
- Treatment Related, TEAEs by maximum grade
- Treatment Related, Serious TEAEs
- Treatment Related, TEAEs leading to study drug withdrawn
- Treatment Related, TEAEs leading to interruption of study drug
- Treatment Related, TEAEs leading to reduction from study drug

In the analysis, the AEs emerged until 70 days after the last dose are intended

Subject data listings of All AEs, SAEs, AEs leading to death, leading to study drug withdrawn or leading to interruption from study drug will be provided.

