9.1.4 Extension Phase

Subjects who complete evaluations at Week 24 of the Treatment Phase will enter the Extension Phase. The investigator or subinvestigator must confirm that all data through Week 24 of the Treatment Phase (the double-blind part) are completely entered into CRFs by Week 26, when the initial assessments in the Extension Phase will be performed. Each subject's assigned treatment group will be blinded until the database of the Treatment Phase is fixed.

The Extension Phase is up to 104 weeks after the start of the study treatment, and subjects will receive an open-label E6011 200 mg every 2 weeks until Week 102. If the investigator or subinvestigator judges that the response to treatment is insufficient in the Extension Phase, administration of E6011 400 mg every 2 weeks will also be allowed (reduction of the dose back to 200 mg after an increase to 400 mg will also be allowed).

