9.7.1.9 Extension Phase Analyses

Similar analyses to those described in the above sections for the Treatment Phase will be conducted for efficacy, pharmacokinetics (except for population PK and PK/PD analyses), biomarker, immunogenicity, and safety endpoints by treatment group of the Treatment Phase.

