3.2 Overall Study Design and Plan

This study is a multicenter, randomized, double-blind, placebo-controlled, parallel-group comparison study. The following 4 treatment groups are selected for the study: E6011 100 mg, 200 mg, 400 mg, and placebo. In the E6011 100 mg, 200 mg, and placebo groups, subjects will receive 100 mg, 200 mg, or placebo at Weeks 0, 1, 2, and every 2 weeks subsequently. In the E6011 400 mg group, subjects will receive 400 mg at Weeks 0, 1, 2, 4, 6, 8, 10 and then 200 mg every 2 weeks subsequently.

The study consists of Screening, Observation, Treatment, Extension, and Follow-up Phases.

Undergoing screening assessments within 42 days prior to the study treatment, subjects with the certain eligibility confirmed in the Observation Phase will be allocated into any of the 100 mg, 200 mg, 400 mg, or placebo groups at a 1:2:2:2 ratio through dynamic allocation using the following factors: C- reactive protein (CRP) level at Screening, Rheumatoid Arthritis (RA) Duration, and Prior Use of Biologics Treatment.

In the Treatment Phase (24 weeks), subjects will receive either E6011 or placebo at Weeks 0, 1, 2, and every 2 weeks until Week 22 in a double-blind manner.

Subjects who complete evaluations at Week 24 of the Treatment Phase will enter the Extension Phase. The Extension Phase is up to Week 104 from the starting of the study treatment, and subjects will receive an open-label E6011 200 mg every 2 weeks until Week 102. When subjects insufficiently respond to the treatment or when their disease relapses in the Extension Phase (show no improvement from Observation Phase in both of tender joint counts (TJC) and swollen joint counts (SJC) at 2 consecutive assessments with an interval of ≥ 1 week), a dose escalation will be allowed.

Follow-up investigations will be conducted on-site 28 days after the completion of the study or the discontinuation of the treatment, and either an on-site or telephone-interview investigation will be conducted 70 days after the last dosing.

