5.4.2 Secondary Efficacy Analyses

For each component of ACR (TJC, SJC, VAS [patient's assessment of pain, patient's global

assessment of disease activity and physician's global assessment of disease activity], functional assessment by subjects (HAQ) and CRP·ESR), DAS28-ESR, DAS28-CRP, SDAI, and CDAI in each visit, the values and the changes from baseline will be summarized by treatment group.

For mTSS, values and changes from baseline will be summarized by treatment group. For DAS28-ESR and DAS28-CRP, frequency and percentage of each classification (no response, moderate response, good response) by EULAR response criteria will be summarized by treatment group and visit in a shift table. For DAS28-ESR, DAS28-CRP, SDAI and CDAI, frequency and percentage of each category (Remission, Low, Moderate, High) will be summarized by treatment group and visit in a shift table.

The mean change from baseline of ACR components, DAS28-CRP, DAS28-ESR, CDAI and SDAI - visit will be displayed by treatment group. ACR response rate - visit will be displayed by treatment group. Cumulative probability of the change from baseline in mTSS will be displayed at week 52 and Week 76.

All efficacy endpoints for the treated subjects will be listed.

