5.6 Safety Analyses

All safety analyses will be performed on the Safety Analysis Set. Safety data, presented by treatment group, will be summarized on an “as treated” basis using descriptive statistics (eg, n, mean, SD, median, minimum, maximum for continuous variables; n [%] for categorical variables). Safety variables include treatment-emergent adverse events (TEAEs), clinical laboratory parameters, vital signs, 12-lead ECG results, chest x-ray, neurological findings, and blood CD4 positive cell count. Day 1 for all safety analyses will be defined as the date of the first dose of study drug.

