5.6.1 Extent of Exposure

The extent of exposure to study drug will be characterized by duration of exposure, number of injection dose and study medication compliance for each treatment group. Definition of analysis items are as follows:

- Duration of exposure (weeks) = (Date of Last Dose - Date of First Dose + 14) / 7
- Number of Injection = Count of records with non-zero treatment
- Study Medication Compliance (%) = Number of Injection / Number of Expected Injection * 100

Subject data listings will be provided.

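### Extension Phase results are grouped by the arm assigned at Week 0, so no prespecified Extension table shows exposure, adverse events or response by the dose actually received

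*SAP*

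**What the plan says.** Protocol 9.7.1.9 sets the Extension grouping. Efficacy, pharmacokinetics and "biomarker, immunogenicity, and safety endpoints by treatment group of the Treatment Phase" are to be analysed as in the Treatment Phase. The SAP, which covers the Extension, follows this:

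- Adverse events (SAP 5.6.2): "The TEAEs will be summarized by treatment group and E6011 overall".
- Safety in general (SAP 5.6): "Safety data, presented by treatment group, will be summarized on an “as treated” basis".
- Efficacy (SAP 5.4.2): "ACR response rate - visit will be displayed by treatment group". Component scores, disease activity indices and mTSS are grouped the same way.
- Exposure (SAP 5.6.1): duration, number of injections and compliance by treatment group, with "Number of Injection = Count of records with non-zero treatment".

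Protocol 9.1.4 puts all subjects on 200 mg every 2 weeks in the Extension. It allows 400 mg every 2 weeks when the investigator judges the response insufficient, and adds that "reduction of the dose back to 200 mg after an increase to 400 mg will also be allowed". SAP 3.2 describes escalation differently, by a joint-count criterion: subjects who "show no improvement from Observation Phase in both of tender joint counts (TJC) and swollen joint counts (SJC) at 2 consecutive assessments".

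**The concern.** In the Extension the column headings placebo, 100 mg, 200 mg and 400 mg record history, not current treatment. An adverse event on 400 mg in a subject randomised to 100 mg is printed under 100 mg. A response reached after escalation is printed as a response of the randomised arm. If harm rose with dose, it would be spread over four columns whose current dosing rule is the same.

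This matters because safety and tolerability are a primary objective, and because prolonged 400 mg dosing happens nowhere else in the trial. The randomised 400 mg arm itself drops to 200 mg at Week 12.

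**Working it through.** The plan gives no number escalated and no time on 400 mg, so it has no figure of its own to reproduce here. Its power statement concerns Week 12 and has no bearing.

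**Step 1. What each label means over time** (Protocol 9.4.1 and 9.1.4).

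| Arm label | Weeks 0 to 10 | Weeks 12 to 22 | Weeks 24 to 102 |
|---|---|---|---|
| Placebo | placebo | placebo | 200 mg, or 400 mg if escalated |
| 100 mg | 100 mg | 100 mg | same |
| 200 mg | 200 mg | 200 mg | same |
| 400 mg | 400 mg | 200 mg | same |

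The last column is identical in every row.

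**Step 2. Search for a dose dimension in the Extension plan.** SAP 5.4.2, 5.6.1, 5.6.2, 5.6.3 and 5.6.4 all group by treatment group. SAP 5.3.4 plans no Extension subgroups. SAP 7 lists changes from the protocol and leaves the grouping alone. SAP 5.5.1 reduces Extension pharmacokinetics to a listing. The as-treated phrase in SAP 5.6 also appears in Protocol 9.7.1.8 for the Treatment Phase and is not defined for dose changes within a subject. The pooled E6011 column mixes both doses, and the SAP does not say whether it includes former placebo subjects. No section counts the subjects escalated, their time on 400 mg, their events on 400 mg, or their response before and after escalation.

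**Step 3. Where 400 mg exposure comes from.** In the Treatment Phase, Weeks 0, 1, 2, 4, 6, 8 and 10 are 7 doses, and 7 × 400 mg = 2,800 mg = 2.8 g. The Extension has (102 − 24)/2 + 1 = 40 scheduled doses, each at 200 or 400 mg. Any 400 mg dosing beyond the 7 doses is therefore in the Extension.

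**Step 4. What an arm total says about escalated subjects** (assumed numbers). Take an arm of 50 with 13 subjects having an event (26%), of whom m subjects were escalated. The number of escalated subjects with an event lies between max(0, 13 − (50 − m)) and min(m, 13).

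| m escalated | Events possible among them | Rate possible |
|---|---|---|
| 5 | 0 to 5 | 0% to 100% |
| 10 | 0 to 10 | 0% to 100% |
| 20 | 0 to 13 | 0% to 65% |
| 30 | 0 to 13 | 0% to 43% |

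The arm total does not identify the rate. Nor does it separate events before escalation from events after it.

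**Step 5. Can masking be complete?** (assumed numbers). If the event rate on 400 mg were twice that on 200 mg, and 30% of person-time in every arm were on 400 mg, each column would show 0.7 × 1 + 0.3 × 2 = 1.3 times the 200 mg rate. The ratio between columns would be 1.0 against a dose ratio of 2.0. The equal 30% forces that result, so this shows only that masking is possible.

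**Step 6. Does the exposure table help?** SAP 5.6.1 does not say whether a record is an administration or an injection. If it is an administration, 200 mg and 400 mg each count once. If it is an injection, Protocol Table 1 allows 400 mg in 4 sites (1 mL each) or 2 sites (2 mL each), and Extension 200 mg in 2 sites or 1. A count of 2 then fits either dose. Neither reading gives mg.

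**The case against.** Reporting by randomised arm follows the protocol and is a coherent description of a treatment strategy in an open-label, descriptive phase. That stands, and the arm tables should stay.

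SAP 5.6.2 also plans tables of adverse events leading to dose reduction. The only Extension reduction that the protocol describes is from 400 to 200 mg, so these tables bear on 400 mg tolerability. The Treatment Phase has a blinded 400 mg arm with its own safety tables. Listings are planned, exploratory analyses are allowed (SAP 5.8), and the table shells are a separate document not available here (SAP 11). All this is true, and it limits the point to prespecified Extension tables. The dose-reduction tables still have no count of escalated subjects as a denominator.

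Four stronger readings are tempting, and the documents do not support them.

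- *That a subject could receive all 40 Extension doses at 400 mg (16 g).* The amendment log shows that before Version 5 (31 August 2018) escalation was allowed once, for 6 doses. The last subject entered the Extension in March 2018. Entry on 31 March is 153 days, or 21.9 weeks, before Version 5, which puts that subject near Week 46. About 11 Extension doses had then been given, at most 6 of them at 400 mg, and about 29 remained. The ceiling is about 35 × 400 mg + 5 × 200 mg = 15 g, and lower for earlier entrants.
- *That SAP 3.2 misstates who received 400 mg.* It is a design summary that classifies no subject, and its joint-count criterion did govern earlier escalations.
- *That 1 of 4 vials scores 100% compliance.* This depends on the unstated record structure.
- *That responses after escalation must count as non-response.* That is a choice of estimand, not an error in the plan.

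**Conclusion.** The point holds for the prespecified Extension tables. The grouping is explicit in Protocol 9.7.1.9, the SAP follows it, and from Week 24 it no longer separates doses. Extended 400 mg dosing, given in a trial with safety as a primary objective, therefore has no planned summary of exposure, events or response.

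The size of any masking is unknown, because the documents do not say how many subjects were escalated or for how long. The ranges in Steps 4 and 5 rest on assumed counts and rates. They show that the arm tables cannot identify a 400 mg effect, not that there is one. A reader might infer that the trial says nothing about 400 mg. It does compare 7 doses of 400 mg with placebo under blinding, and the gap concerns longer dosing only. This should be changed, but it does not touch the Week 12 primary analysis.

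**What to change.** Keep the randomised-arm tables and add the following to the SAP.

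1. **Exposure (5.6.1).** Number ever on 400 mg, number on 400 mg at each visit, and person-time and cumulative mg at 200 mg and at 400 mg, by arm and overall.
2. **Adverse events (5.6.2).** TEAEs, serious TEAEs and TEAEs leading to withdrawal, by most recent dose level at onset, with exposure-adjusted rates. State that events up to 70 days after the last dose go to the last dose level received. Caution about carry-over after a dose change: Protocol 9.2 equates 70 days with about 5 times the longest half-life, so 70/5 = about 14 days. Say whether E6011 overall includes former placebo subjects.
3. **Compliance (5.6.1).** Define a record as an administration or an injection, and report mg given divided by mg planned.
4. **Efficacy (5.4.2), optional and supplementary.** ACR response split by whether the subject had already escalated.
5. **Escalation wording.** Reconcile SAP 3.2 with Protocol 9.1.4 and state which wording applied in which period.

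Label items 1, 2 and 4 descriptive and non-randomised, because escalation follows poor response. The cost is SAP wording and a few tables. Protocol 9.4.8 and 11.5 already have dosing status, incomplete doses and reasons for dose changes recorded in the CRF. If the Extension database is already locked, the same tables can be run under SAP 5.8 and labelled exploratory.

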9.3.3 Removal of Subjects From Therapy or Assessment

The investigator or subinvestigator may withdraw the subject from the study at any time for safety or administrative reasons. The subject may stop study drug or withdraw from the study at any time for any reason.

All subjects who discontinue the study should be followed for procedures/assessments at discontinuation as specified in the Schedule of Procedures/Assessments ([Section 9.5.2.1, Table 4](#); also see [Section 9.5.5](#) “Completion/Discontinuation of Subjects” for more information).

A subject will be withdrawn from the study under any of the following circumstances.

1. Occurrence of AE that made it difficult to continue the study
2. Subject is pregnant.
3. Subject's ineligibility is confirmed.
4. Concomitant medication or therapy cannot be continued in accordance with the protocol.
5. Required surgical operation on arthritic disorder
6. Diagnosed with malignant tumor
7. Tested positive in tuberculosis test (QuantiFERON TB® Gold Test or T-SPOT®.TB Test)
8. Tested positive for any of the following: HIV, HBs antigen, HBV DNA, HCV antibody, HTLV-1 antibody, or syphilis (except if false positive for the syphilis test)
9. When the investigator or subinvestigator judges that efficacy of E6011 is insufficient, after the date Version 6 of the protocol was approved by IRB
10. When the investigator or subinvestigator judges that there are other effective treatment options available besides continuing this study, after the date Version 6 of the protocol was approved by IRB

Withdrawal from the study will be considered if a subject skips 3 consecutive administrations.

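### Extension adverse events are planned only as crude percentages although time at risk can differ several-fold between subjects; first-event rates per patient-year should be added

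*SAP*

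**What the plan says.** SAP 5.6.2 lists the treatment-emergent adverse event (TEAE) tables: all, by maximum intensity or grade, serious, leading to withdrawal, interruption or reduction, and the treatment-related versions. All take one form: "The incidence of follow TEAEs will be reported as the number (percentage) of subjects with TEAEs by SOC and PT". The counting rule is "A subject will be counted only once within an SOC and PT, even if the subject experienced more than 1 TEAE" within a given class and term. The window closes on each subject's own date: "In the analysis, the AEs emerged until 70 days after the last dose are intended". Protocol 9.7.1.8.2 likewise gives number and percentage only. Neither document plans patient-years, an exposure-adjusted rate, time to first event or counts by interval.

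The time frame comes from four other places:

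- **Dosing** (SAP 3.2): "subjects will receive an open-label E6011 200 mg every 2 weeks until Week 102".
- **Clock** (SAP 5.6): "Day 1 for all safety analyses will be defined as the date of the first dose of study drug". TEAEs are judged against the pretreatment state, and no new start at Week 24 is stated.
- **Denominator** (SAP 5.2.1): one dose and one safety assessment in the Week 24 to 104 period are enough.
- **Exposure** (SAP 5.6.1): "Duration of exposure (weeks) = (Date of Last Dose - Date of First Dose + 14) / 7". It is summarised by group, but no TEAE table uses it.

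Protocol 9.3.3 lets a subject stop at any time for any reason. Version 6 added two investigator-judged withdrawal reasons: insufficient efficacy, and "When the investigator or subinvestigator judges that there are other effective treatment options available besides continuing this study".

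**The concern.** A subject whose last dose is at Week 24 and one dosed to Week 102 carry equal weight in the denominator, although the second is observed far longer. Shorter observation can only lower the number of subjects with an event. A crude percentage therefore reflects both how often events occur and how long subjects stayed. If retention differs between the original arms, the arm with shorter follow-up shows a lower figure for reasons unrelated to the drug.

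Safety and tolerability is a primary objective, and after Version 6 safety is nearly all that is still assessed. The protocol names vasculitis and PML as potential risks. For rare or late events, the percentage is close to proportional to follow-up, so those are the events most affected.

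**Working it through.** **The plan's own figure.** With the last dose at Week 102 (day 714 after first dose), the SAP 5.6.1 formula gives (714 + 14) / 7 = 104 weeks. This matches the protocol's 24 + 80 weeks.

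**Time at risk for adverse events.** This is the last-dose week plus 70/7 = 10 weeks, taking the Week 24 open-label dose as the earliest that qualifies a subject.

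| Clock starts | Last dose Week 24 | Last dose Week 102 | Ratio |
|---|---|---|---|
| First dose | 24 + 10 = 34 weeks | 102 + 10 = 112 weeks | 3.3 |
| Week 24 | 10 weeks | 112 − 24 = 88 weeks | 8.8 |

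The exposure summary adds 14 days after the last dose, not 70, so it is not the person-time over which events are counted.

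**Illustration.** The documents give no event rate and no stopping pattern by arm, so these inputs are assumed. The hazard h is constant and equal in both arms, and stopping is unrelated to events. In arm X 10%, and in arm Y 40%, stop at one early week; the rest are dosed to Week 102.

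The probability of a first event by t weeks is F(t) = 1 − exp(−h·t/52). The crude percentage is w·F(early) + (1 − w)·F(full), where w is the share stopping early.

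With h = 0.5 per patient-year and the clock from first dose, F(50) = 38.17%, F(86) = 56.26% and F(112) = 65.94%.

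- **Stops at Week 40 (50 weeks at risk).** X: 0.1 × 38.17 + 0.9 × 65.94 = 63.16%. Y: 0.4 × 38.17 + 0.6 × 65.94 = 54.83%. Gap 8.3 points.
- **Stops at Week 76 (86 weeks at risk).** X: 0.1 × 56.26 + 0.9 × 65.94 = 64.97%. Y: 0.4 × 56.26 + 0.6 × 65.94 = 62.07%. Gap 2.9 points.

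Gaps at other hazards, clock from first dose:

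| Hazard per patient-year | Stops at Week 40 | Stops at Week 76 |
|---|---|---|
| 0.1 | 3.1 points | 1.2 points |
| 0.3 | 6.8 points | 2.5 points |
| 0.5 | 8.3 points | 2.9 points |
| 1.0 | 8.0 points | 2.3 points |

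With the clock from Week 24 and h = 0.5, F(26) = 22.12% and F(88) = 57.09%. Stops at Week 40 then give 53.6% against 43.1%, a gap of 10.5 points.

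**What a rate would show.** Under a constant hazard, expected person-time to first event equals expected first events divided by h. For the Week 40 case from first dose, per 100 subjects, this is 63.16 / 0.5 = 126.3 patient-years in X and 54.83 / 0.5 = 109.7 in Y. Both arms show 50 per 100 patient-years, so the artificial gap disappears.

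**When Version 6 can act.** Protocol Section 7 says the last subject entered the extension (Week 24) in March 2018 and that all had completed 52 weeks of E6011 by March 2019. Version 6 is dated 25 March 2019. Subjects still on study were then at about 24 + 52 = Week 76 or later. The new reasons can remove at most about 102 − 76 = 26 weeks of dosing.

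**The case against.** The strongest reply is that these tables are descriptive. From Week 24 every arm receives open-label E6011, there is no concurrent control, and the SAP plans no formal comparison. The placebo-controlled safety comparison belongs to the 24-week phase. Exposure (SAP 5.6.1), discontinuations with reasons (SAP 5.2.2) and event listings are already planned by group or subject, so a gross imbalance would be visible. Stopping is also not independent of events. A subject withdrawn because of a TEAE has already been counted, and front-loaded events are little diluted by later dropout.

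Most of this stands and limits the size of the point. It does not remove it. A descriptive table still needs a denominator that can be read across columns, and group-level exposure does not correct the percentage for each class and term.

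A reader might go further and infer that Version 6 withdrawals drive the problem. The dates do not support that: those reasons act only from about Week 76, where the illustrated gap is 2.9 points, and they cannot produce stops at Week 40. A reader might also take 112 weeks as the length of the window. That follows from the SAP's literal clock, but an extension-only window of up to 88 weeks is an equally possible intention.

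**Conclusion.** The point holds as a cheap improvement. The plan allows time at risk to vary about 3-fold (from first dose) or 9-fold (from Week 24), and nothing in the TEAE tables accounts for it. The direction is general: less follow-up lowers a first-event percentage. The size is conditional. In the illustration at 0.5 per patient-year from first dose, it is 8.3 points for Week 40 stops and 2.9 for Week 76 stops. Both rest on an assumed constant hazard, an assumed 10% against 40% split, and stopping unrelated to events.

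The documents do not support the stronger inference that one arm of this trial will look safer than it is. They give no stopping or event rates by arm, so imbalance is possible but not shown. Nor would a real excess necessarily be hidden. With a 30% higher true hazard in arm Y (0.65 against 0.5), Week 40 stops give 63.8% against 63.2%, but Week 76 stops give 71.6% against 65.0%, leaving the excess visible.

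**What to change.** In SAP 5.6.2 keep the percentages. For any, serious and treatment-related TEAEs, and for class and term where counts allow, add the number of subjects with a first event, patient-years at risk, and the rate per 100 patient-years with an exact Poisson 95% CI. Give these by original arm and for E6011 overall.

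State the clock. For extension tables, person-time runs from the first open-label dose at Week 24 to the first event or 70 days after the last dose, and only events with onset in that window count. In any pooled E6011 column that starts earlier, begin each subject's time at the first E6011 dose, so that placebo time is excluded.

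The cost is SAP wording and a few derived columns from dosing and event dates that the planned analyses already use. No clinical procedure changes. If the SAP is already final, Protocol 9.7.5 provides for a documented revision described in the study report. The downside is that rates assume a roughly constant hazard and intervals will be wide in arms of 25 to 50 randomised subjects, so the rates should be read beside the percentages.
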